5.6 Post-Treament Follow-Up

Patients will be followed for up to 60 months after completion of radiation or until death to assess intervention-related tolerance. See study calendar.

- 1. Month 1 visit (30 days after completion of all radiation therapy, +/- 14 days)
- 2. Month 3 visit (90 days after completion of all radiation therapy, +/- 28 days)
- 3. Long Term Follow-Up Visits: Month 6 (M6), Month 9 (M9), Month 12 (M12), Month 18 (M18), Month 24 (M24), Month 36 (M36), Month 48 (M48), and Month 60 (M60) (calculated from completion of all radiation therapy, +/- 28 days)

Assessments include:

- Focused skin exam
- Adverse event/toxicity evaluation, including CTCAE version 5 evaluation of radiation dermatitis with note of components (erythema, epilation, fibrosis, etc)
- SkinDex16 guestionnaire
- Photographic documentation of skin reaction with dermatologist's evaluation of CTCAE version 5 from this photography

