2.1.2 Secondary Objectives

2.2.2.1

To assess the highest grade of CTCAE version 5 radiation dermatitis during radiation treatment

2.2.2.2

To assess the time to occurrence of CTCAE version 5 grade 2 or higher acute radiation dermatitis.

2.2.2.3

To assess the time to healing if CTCAE version 5 grade 2 or higher acute radiation dermatitis develops.

2.2.2.4

To evaluate quality of life via acute and long-term symptoms and symptom scores utilizing the SkinDex16 scoring system.

2.2.2.5

To evaluate the threshold dose at which RD appears in either arm, utilizing skin dose tracking structures (V20 to V80 in 5 Gy increments reaching skin shell contours of "skin minus 3 millimeters" and "skin minus 5 millimeters")

2.2.2.6

To evaluate the threshold dose at which RD appears in either arm, using the same metrics as in 2.2.2.5, but with a new simulation scan in the last week of radiotherapy

2.2.2.7

To evaluate the effect of dermaprazole on inflammatory markers: CRP, TNFa, IL-1b, IL-6, by measuring values before, during, and after treatment. We expect this to give further evidence for the mechanism of action of dermaprazole.

Page 4 of 23

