Figure 1: Topical application of Dermaprazole Improves skin appearance in a model of radiation-induced dermal inflammation & fibrosis. Mice were irradiated (2 x 15 Gy) on Days 0 & 7. Dermaprazole, vehicle (base) cream, or the corticosteroid hydrocortisone were applied once a day on the indicated days (D1-D30 for prophylactic group & D10-D30 for therapeutic group). Representative images from the same animals are shown (n=10 animals/group).

mortar, wetting with propylene glycol, and mixing with a transdermal base (i.e., Lipoderm). Notably, our LC-MS study showed that a relatively low strength of Dermaprazole (1-2%) was highly stable and biologically active in modulating

esomeprazole target genes.

Accordingly, we evaluated the efficacy of this formulation in a mouse model of RD in a prophylactic and therapeutic settings in the presence of corticosteroid control. Remarkably, our study showed that while 90% of the animals in the

[figure not shown]

Figure 2: H&E stain showing that topical delivery of Dermaprazole improves skin histology in an animal model of radiation-induced dermal inflammation & fibrosis. Mice were irradiated (2 x 15 Gy) on Days 0 & 7. Dermaprazole, vehicle (base) cream, or the steroid hydrocortisone (1.0%) were applied once a day on the indicated days (D1-D30 for prophylactic group & D10-D30 for therapeutic group). Dermal thickening is observed in the Vehicle group and profound loss of skin integrity is seen by Day 30 in the steroid-treated group. Representative images are shown at 20X mag.

corticosteroid group had grade II or higher dermatitis, topical PPI mitigated the radiation dermatitis in most of the animals with only 20% showing grade II or higher radiation dermatitis (Figure 1). We also observed that Dermaprazole use led to significantly lower ulceration, necrosis, inflammation, and fibrosis (Figure 2 and Figure 3). Overall, most Dermaprazole treated animals showed complete or nearly complete closure of the

wounds within 4 weeks following exposure to ionizing radiation (Pham, et al., 2019).

[figure not shown]

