5.4 Intervention

Head and neck radiation treatment will follow standard practice. Variations (dose adjustments, delays, etc) that follow standard clinical practice are allowed and are not considered deviations, though these will be recorded to assess for interference.

Patients will be managed with twice daily prophylactic use of the proposed intervention (Dermaprazole) topical cream for radiation dermatitis or Aquaphor. The amount of cream or Aquaphor will be 2cc per application and will be measured in pre-filled capped syringes for every application.

The Dermaprazole topical cream will be manufactured by Village Pharmacy in Houston. After the product is compounded it will be overnight shipped to the Mays Cancer Center Pharmacy in insulated shipping containers with temperature monitors. The cream will be

Page 9 of 23

stable for a minimum of 60 days in airtight containers under refrigerated conditions ($2^{\circ} - 8^{\circ}$ C) and is stable at controlled room temperature for at least 1 week. Room temperature is 20° C – 25° C (excursions permitted between 15°C and 30°C). A one to three week supply of the cream will be dispensed to the subject during study participation, with the exception that a 2 - 3 week supply will be provided at the time of CT Simulation (determined by the anticipated radiation start date). The same method will be used for the dispensing of the Aquaphor except that refrigeration will not be done in the pharmacy.

Patients will be instructed to apply the cream/Aquaphor along the area exposed to radiation from the day of simulation to two weeks after completion, correlating with the acute phase of radiation dermatitis. If the time from CT Simulation to start of radiation is greater than 2 weeks then the patient may be instructed to start the cream/Aquaphor 2 weeks prior to the anticipated start of radiation rather than at the time of CT Simulation. In the event of a delay from the time of CT simulation to the start of XRT, if the patient has no more than 3 days of interruption of the cream, this will not be considered a violation of the protocol. An interruption longer than 3 days will be considered a minor deviation. Patients who develop moist desquamation in the radiation treatment area may be prescribed a topical antibiotic or other standard of care treatment if indicated. Subjects will be instructed to not use other lotions, creams or any other products in the radiation treatment area without the study doctor's approval.

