6 TREATMENT EVALUATION

6.1 Calendar of Study Assessments & Testing

		Head/Neck RT(Weekly) ^a								
	Baseline	Week 1	Week 2	Week 3	Week 4	Week 5	Week 6	Week 7	Week 8	Week 9 ^h
SCREENING										
Written Informed Consent	Х									
Inclusion/Exclusion Criteria	Х									
PHYSICAL										
Comprehensive History and Physical (ECOG only at Baseline)	Х									
Focused Skin Exam (Radiation Oncologist)	Х	Х	Х	Х	Х	Х	Х	Х		
Medical Photography ^d	Χ	X	Х	Х	Х	Х	Х	Х		
ASSESSMENTS										
CTCAE Version 5 Radiation Dermatitis (Radiation Oncologist)		Х	Х	Х	Х	Х	Х	Х		
CTCAE Version 5 Radiation Dermatitis (Blinded – Dermatologist)		Х	Х	Х	Х	Х	Х	Х		
Adverse Events/Toxicity		Х	Х	Х	Х	Х	Х	Х		
SkinDex16 Questionnaire	Χ	Х	Х	Х	Х	Х	Х	Х		
TREATMENT										
CT Simulation	Х							Χg		
XRT		Х	Х	Х	Х	Х	Х	Х		
Dermaprazole or Aquaphor ^c	Х	Х	Х	Х	Х	Х	Х	Х	Х	Х
Compliance Assessment	X ^f	X	Х	Х	Х	Х	Х	Х		Х
LAB DRAW										
Serum Pregnancy Test if Woman of Child-Bearing Potential	Х									
WBC, Hgb, ALT, AST, creatinine, calcium captured from clinical labse	Х	Х	Х	Х	Х	Х	Х	Х	Х	Х
Research Blood Draw to Central Lab: CRP, TNFa, IL-1b, IL-6	X							Xp		Х

- (a) Weekly assessments to be performed within +/- 3 days of the end of each week (defined by a period of 5 treatments).
- (b) In the last week of radiotherapy, may be different than week 7 $\,$
- (c) See Section 5.3 for detailed instructions regarding Dermaprazole and Aquaphor
- (d) Photos will be taken with a Canon EOS Rebel T7 DSLR Camera with 18-55mm Lens. Photos will be uploaded to a protected research folder directly from the camera and the dermatologist will have access to the folder. The photos will be de-identified and labeled with study case number.
- (e) WBC, Hgb, ALT, AST, creatinine and calcium data will be obtained from standard care clinical labs during treatment. If labs are not being drawn then they will not be obtained for the study.
- (f) Compliance assessment may be performed by telephone by research staff from Baseline to start of XRT
- (g) CT Simulation to be done anytime during the last 7 days of radiation treatment
- (h) Week 9 is defined as 2 weeks post last radiation treatment ± 5 day

Page 12 of 23

	Post-Treatment Assessment		Long Term Follow-Up Up to 60 months post-tx		
	Month 1 30 days post-tx ⁱ	Month 3 90 days post- ^{txj}	Every 3 Months M6, M9, M12j	Every year M24, M36, M48, ^{M60j}	
PHYSICAL					
Focused Skin Exam (Radiation Oncologist)	X	X	X	X	
Medical Photography	X	X	X	X	
ASSESSMENTS					

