8.3 Analysis of Primary and Secondary Endpoints

Descriptive and summary statistics will be computed for demographic and clinical data of all subjects enrolled in the study to describe the study sample.

Toxicity will be reported as the frequency of each adverse event according to the CTCAE version 5.0 as well as the grade of each recorded adverse event (38). Generally, adverse events in this system are graded from 1 to 5, with 1 corresponding to either mild or asymptomatic clinical manifestations of toxicity and 5 corresponding to death related to the

Page 15 of 23

adverse event (see Appendix 2). Clinically relevant toxicity will be defined as grade 2 or higher, while severe toxicity will be defined as grade 3 or higher. Acute toxicity will be defined as adverse events that occur during or within 90 days after completing radiation therapy. We will consider this intervention safe if there is a grade 1 toxicity rate of <50%, a grade 2 or higher toxicity rate of <10% and no grade 3 or higher events.

Percentages of patients enrolled per month will be recorded. If the enrollment time exceeds 24 months, the study will be considered not feasible as written. Percentage of patients not enrolled will be summarized by cause.

Quality of life will be measured with the use of SkinDex16 questionnaires filled out by the patient at baseline, throughout treatment, at the completion of radiation treatment, and at each follow up visit subsequently. We will also consider the compliance to questionnaire completion and within questionnaires completion rates. This will be reported as the average proportion of questions within each form completed properly, without errors. As long as the rates are not below the minimum threshold defined above, the study will be considered feasible.

All analyses outside of the primary endpoint will be considered exploratory in nature. Chi square and t-test will be used to evaluate differences in categorical and numerical values between arms. Subgroup analyses for BMI, total dose, and comorbidity will be conducted. We will also evaluate the incidence of RD for specific radiation skin dose stratification by reviewing the V20 to V80 in 5 Gy increments reaching a skin shell representing the thickness between the skin and the "skin minus 3 millimeters" and the "skin minus 5 millimeters." This will be done on both the original dosimetry as well as a recalculated plan from the resimulation scan.

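### Time to healing of grade 2+ dermatitis is interval-censored by the visit schedule after radiation, and section 8.3 names only a t-test for numerical outcomes

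*Combined protocol and SAP*

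**What the plan says.** Section 2.1.2, item 2.2.2.3, sets the objective: "To assess the time to healing if CTCAE version 5 grade 2 or higher acute radiation dermatitis develops". It gives no definition of healing, no time origin and no dating rule.

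During radiation, the section 6.1 calendar marks skin exam, photography and both CTCAE gradings every week through Week 7, with "Weekly assessments to be performed within +/- 3 days of the end of each week". All four rows are blank at Weeks 8 and 9. A Week 9 contact exists ("Week 9 is defined as 2 weeks post last radiation treatment ± 5 day"), but it carries study product, compliance, clinical labs and the research blood draw, with no skin grading.

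Grading resumes at the "Month 1 visit (30 days after completion of all radiation therapy, +/- 14 days", followed by the "Month 3 visit (90 days after completion of all radiation therapy, +/- 28 days" (section 5.6).

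On analysis, section 8.3 says "Chi square and t-test will be used to evaluate differences in categorical and numerical values between arms". Section 8 names no time-to-event or interval-censored method.

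**The concern.** When an event is seen only at visits, its date is known only to lie between the last visit without it and the first visit with it. Here that interval is about a week for skin that heals during radiation and weeks to months for skin that heals afterwards. Section 5.4 has patients apply the product "from the day of simulation to two weeks after completion, correlating with the acute phase of radiation dermatitis", so by the protocol's own account the acute phase ends inside the ungraded stretch.

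If the first healed visit is entered as the healing date and the arms are compared by t-test, three things follow. Reported healing times are too long. Part of the spread comes from appointment dates. Patients who just miss being healed at Month 1 are recorded at about day 90. A real difference between arms could then be missed, and the size of any observed difference could not be read at face value.

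**Working it through.** **The plan's own figure.** The documents state no figure for time to healing. The sample size of about 39 in section 8.2 reproduces (65% v 20%, two-sided 0.05, 80% power, 2:1, no continuity correction: 13 + 26 = 39). It concerns the primary endpoint, and is used here only for its event rates.

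**Gaps between gradings**, in days from the last fraction, taking the last weekly exam as due on that day:
- Last weekly exam: −3 to +3. Month 1: 30 ± 14, so 16 to 44. Month 3: 90 ± 28, so 62 to 118.
- Last weekly exam to Month 1: 16 − 3 = 13 up to 44 + 3 = 47 days.
- Month 1 to Month 3: 62 − 44 = 18 up to 118 − 16 = 102 days.
- Between weekly exams: nominally 7 days, at most 7 + 3 + 3 = 13.

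**Patients contributing**, at the section 8.2 rates: 30 × 0.20 = 6 on Dermaprazole and 15 × 0.65 = 9.75, about 10, on Aquaphor.

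**Simulation.** Assumptions, none of them from the documents: grade 2+ dermatitis is still present at the end of radiation; time to healing from then is lognormal; visits are uniform within their windows; the first scheduled grading after true healing is taken as the healing date. Results at log-SD 0.4 / 0.6:

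| True median (days) | First seen healed at Month 1 | Recorded median (days) | Excess (days) |
|---|---|---|---|
| 10 | 98% / 94% | 30.5 / 31.4 | 20.5 / 21.4 |
| 14 | 93% / 86% | 32.0 / 33.4 | 18.0 / 19.4 |
| 21 | 74% / 68% | 36.9 / 38.1 | 15.9 / 17.1 |
| 28 | 53% / 52% | 43.0 / 43.3 | 15.0 / 15.3 |

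Nearly all the rest are first seen healed at Month 3.

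**Comparison of arms.** A t-test compares means. The true lognormal mean is median × exp(SD²/2). At log-SD 0.4 the factor is exp(0.08) = 1.083, so 14 v 21 gives 15.2 v 22.7 and a difference of 7 × 1.083 = 7.6 days. With 6 v 10 patients, log-SD 0.4 and the equal-variance t-test:

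| True medians | Median difference, true → recorded | Mean difference, true → recorded | Power, exact dates → visit dates |
|---|---|---|---|
| 14 v 21 | 7 → 5 | 7.6 → about 12 | 38% → 7% |
| 10 v 20 | 10 → about 6 | 10.8 → 14.2 | 80% → 8% |
| 14 v 28 | 14 → 11 | 15.2 → 25.6 | 80% → 38% |

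The mean difference grows because the slower arm has more patients first seen healed at Month 3. Power still falls because the spread grows more: for 14 v 21, the SDs rise from about 6 and 9 days to about 18 and 28.

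The power loss depends on these choices. Rerunning the same simulation at log-SD 0.6 gives 15% → 7% (14 v 21) and 39% → 10% (10 v 20). The unequal-variance t-test at log-SD 0.4 gives 46% → 18% and 87% → 21%.

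**The case against.** *Events are followed to resolution.* Section 10.5 follows related ongoing events to resolution or the end of follow-up, and section 5.7 continues photographs of in-field events until resolution. Both could yield extra observations. Neither sets an interval or refers to the healing objective, and the section 5.7 text sits under early discontinuation or study termination. The gap in scheduled grading stands.

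*The plan never says that the visit date is the healing date.* That is correct. The sentence on the t-test is generic, so the charge is that the plan is silent and the one method it names for numerical outcomes is unsuitable. It is not that a wrong rule has been written down.

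*The size is assumed.* Also correct. A reader might infer that dermatitis heals just as grading thins out, so that the recorded time is essentially the Month 1 date. The documents do not establish this. At a true median of 28 days only about half are dated at Month 1. The rationale's closure of "wounds within 4 weeks following exposure to ionizing radiation" describes mice, counted from exposure, and does not time healing after a human radiation course.

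*Modelling cannot recover data that were never collected.* True, and with about 16 patients an interval-censored comparison will be imprecise. It will show that imprecision, which a t-test on visit dates would not.

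*The endpoint is minor.* It is one of seven secondary objectives, and section 8.3 treats everything outside the primary endpoint as exploratory. This limits the severity but does not remove the point.

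**Conclusion.** The point holds in a limited form. Healing after radiation is interval-censored with gaps of 13 to 47 and then 18 to 102 days, which follows from the schedule alone. The plan neither defines healing nor names a method suited to such data.

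The consequences depend on assumed healing times. For medians of 10 to 28 days and log-SD 0.4 to 0.6, 52% to 98% are first seen healed at Month 1 and recorded medians are about 15 to 21 days too long. In the three comparisons at log-SD 0.4, a t-test on visit dates loses more than half its power.

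A reader might also infer that the schedule shrinks the difference between arms. That is true of the medians in these scenarios. It is false of the means, which a t-test compares and which move further apart. The defensible statement is that the mean difference is distorted and its precision is poor.

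Severity is low to moderate: the endpoint is secondary and exploratory, and the primary endpoint and sample size are untouched.

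**What to change.** In section 8.3, define healing as an interval: after the last exam at grade 2 or higher and by the first exam below grade 2. State the time origin and which of the two gradings counts (radiation oncologist or blinded dermatologist). Replace any t-test on visit dates with an interval-censored analysis, for example a Turnbull estimate by arm with an interval-censored Weibull model for the comparison. Report it as exploratory, with its uncertainty.

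A patient-reported closure date, if collected, should be descriptive only. It relies on recall, the protocol describes no blinding of patients, and skin can be closed yet still grade 2, because section 7 counts moderate to brisk erythema and moderate edema as grade 2.

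The cost is SAP wording, slightly more analysis, and wider intervals with about 16 patients.

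An optional addition, which needs a calendar change, is skin grading and a photograph at the existing Week 9 contact. At log-SD 0.4 and a true median of 14 days, this brings the recorded median from 32.0 to 18.9 days. At 21 days or more the gain is small, so the interval-censored analysis is needed either way.

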3.1 Study Disease

Radiation dermatitis is an expected complication of radiotherapy that can lead to worse patient-reported quality of life during treatment and worse cosmesis, particularly in obese patients. Patients within the Bexar County Health System are more likely to have risk factors associated with radiation dermatitis, including obesity and diabetes. While our mostly low socioeconomic status patients stand to benefit the most from upfront therapy in order to prevent later cancer-related morbidity and mortality, they are also more likely to suffer from acute treatment-related morbidity, including radiation dermatitis.

Given the unmet medical need for therapies to address radiation dermatitis, our basic science team has been investigating candidate drugs to mitigate the problem. After screening a library of 130,000 compounds, we found that proton pump inhibitor (PPIs) have previously unrecognized yet potent effect in modulating inflammation and fibrosis induced by chemotherapy and ionizing radiation. Radiation-induced dermatitis occurs in most patients following radiotherapy. According to the NCI-CTCAE (Services, 2017) and RTOG (J. D. Cox, 1995) scoring systems, mild dermatitis (Grade I) is characterized by mild redness (erythema), epidermal thickening (hyperkeratosis) or dry desquamation and appears shortly after initiation of T. Moderate dermatitis (Grade II) occurs within two weeks of radiotherapy and manifests painful and intense erythema, loss of hair from the root (epilation), blisters and edema. Of note, the presence of grade II toxicity is generally regarded as clinically significant toxicity. In severe dermatitis (Grade III and IV), moist desquamation occurs excessively and may lead to persistent inflammation, full-thickness skin necrosis and severely painful ulceration that is prone to infection. The acute effects occur almost immediately at radiation doses between 2 and 40 Gray (2-40 Gy) whereas chronic effects occur several months-to-years after exposure to high radiation doses (> 45 Gy) and typical skin changes include atrophy, scarring and spider veins (telangiectasia) (S. R. Hymes, 2006).

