CTCAE Version 5 Radiation Dermatitis (Radiation Oncologist)	Х	Х	Х	Х	
CTCAE Version 5 Radiation Dermatitis (Blinded – Dermatologist)	X	X	Х	X	
Adverse Events/Toxicity	X ^k	X ^k	X ^k	X ^k	
SkinDex16	Х	Х	Х	X	

Note: Timing of post-treatment visits is from the completion of radiotherapy

- (i) To be completed within +/- 14 days
- (j) To be completed within +/- 28 days
- (k) See Section 10.5.

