6.2 Treatment Evaluation

A general history and physical must be done within 12 weeks prior to registration. Pathologic diagnosis of the tumor must be done within 6 months prior to registration.

After completion of chemoradiation, patients will be seen at one, three, six, nine, and twelve months for an adverse events/toxicity check and clinical evaluation of skin by a radiation oncologist during the first year. Subsequent evaluation at two, three, four and five years will be completed to assess for long-term adverse events/toxicities. Medical photographs will be obtained for review by a board-certified dermatologist. See study calendar.

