7 MEASUREMENT OF EFFECT

Rates and severity of radiation-related toxicity will be defined using NCI Common Terminology Criteria for Adverse Events version 5. These will be used in assessment by the treating radiation oncologist as well as during blinded review by the dermatologist.

The following definitions will be used:

• Grade 1: Mild; asymptomatic or mild symptoms; clinical or diagnostic observations only; intervention not indicated

Page 13 of 23

- o Faint erythema or dry desquamation
- Grade 2: Moderate; minimal, local or noninvasive intervention indicated; limiting ageappropriate instrumental activities of daily living (ADL)
 - o Moderate to brisk erythema; patchy moist desquamation, mostly confined to skin folds and creases; moderate edema
- Grade 3: Severe or medically significant but not immediately life-threatening; hospitalization or prolongation of hospitalization indicated; disabling; limiting self-care ADL
 - Moist desquamation in areas other than skin folds and creases; bleeding induced by minor trauma or abrasion
- Grade 4: Life-threatening consequences; urgent intervention indicated.
 - O Skin necrosis or ulceration of full thickness dermis; spontaneous bleeding from involved site; skin graft indicated
- Grade 5: Death related to adverse event.

Compliance to intervention and use of other topical agents will be documented qualitatively during weekly assessments. Patient's effect on quality of life will be evaluated using SkinDex 16 (Appendix 1).

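### From Month 6 to Month 60 the only blinded skin assessment is the radiation dermatitis grade, whose printed descriptors name none of the late skin changes the plan expects

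*Combined protocol and SAP*

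**What the plan says.** **The blinded reader's task.** Section 5.6 lists, for every post-treatment visit, "Photographic documentation of skin reaction with dermatologist's evaluation of CTCAE version 5 from this photography". No CTCAE term is named. In the calendar (6.1) the only row marked as blinded is "CTCAE Version 5 Radiation Dermatitis (Blinded – Dermatologist", ticked in all four post-treatment columns up to Month 60.

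**The scale.** Section 7 gives CTCAE version 5 definitions and states: "These will be used in assessment by the treating radiation oncologist as well as during blinded review by the dermatologist". Each grade has a general severity definition followed by a skin descriptor. Grade 1 is "Faint erythema or dry desquamation". Grade 2 is "Moderate to brisk erythema; patchy moist desquamation, mostly confined to skin folds and creases; moderate edema". Grade 3 is moist desquamation beyond the folds, or bleeding after minor trauma. Grade 4 is "Skin necrosis or ulceration of full thickness dermis; spontaneous bleeding from involved site; skin graft indicated".

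**The purpose of the late visits.** Section 6.2: "Subsequent evaluation at two, three, four and five years will be completed to assess for long-term adverse events/toxicities". On chronic effects, section 3.1 says that "typical skin changes include atrophy, scarring and spider veins (telangiectasia". Section 10.3 adds long-term fibrosis.

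**The other route.** The toxicity line in 5.6 asks for a note of components, fibrosis among them. Section 10.5 requires recording of pigmentation change, epilation, fibrosis and scarring lasting beyond 6 months, whatever the perceived cause. Sections 8.3 and 10.2 have adverse events graded by CTCAE version 5.

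**The concern.** The late visits exist to look for long-term toxicity, and the plan has photographs read blind at each of them. The one thing the calendar asks the blinded reader to grade is described by erythema, desquamation, edema, bleeding, necrosis and ulceration. The changes the plan itself expects late are different ones.

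At stake is whether late skin changes can be compared between arms without the assessor knowing the arm. Under 10.3, attribution of an adverse event to the radiation or to the study product is decided by the treating investigator or Principal Investigator, and nothing describes either as blinded. This matters more here than in most pilots, because section 3.2 gives an antifibrotic effect as part of the rationale and 10.3 says the cream has not been tested in humans.

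**Working it through.** The plan gives no figure on this point, so there is none to reproduce; the sample-size calculation plays no part. The check sets the named late changes beside the places where they could be captured.

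| Late change | Named in | In section 7 skin descriptors (blinded grade) | Named in a follow-up assessment |
|---|---|---|---|
| Atrophy | 3.1 | No | No |
| Scarring | 3.1, 10.5 | No | Yes, 10.5 |
| Telangiectasia | 3.1 | No | No |
| Fibrosis | 5.6, 10.3, 10.5 | No | Yes, 5.6 (note) and 10.5 |
| Pigmentation change beyond 6 months | 10.5 | No | Yes, 10.5 |

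1. **Blinded capture.** 0 of 5 named changes appear in the section 7 skin descriptors. Counting only the three in section 3.1, the match is 0 of 3.
2. **Any named capture.** 3 of 5 are named in a follow-up assessment. The other two, atrophy and telangiectasia, are named in none, although the component list in 5.6 is open-ended.
3. **Graded or not.** The component note in 5.6 is not itself a grade. Events recorded under 10.5 are graded, because 10.2 and 8.3 apply CTCAE grades to recorded adverse events. What is missing for these three changes is blinding, not grading.
4. **Source of the restriction.** Section 5.6 says only CTCAE version 5. The limit to dermatitis comes from the row label in 6.1 read with section 7. The three places do not say the same thing.
5. **Number of readings.** The calendar has seven visits from Month 6 (M6, M9, M12, M24, M36, M48, M60). With 45 patients, 7 × 45 = 315 scheduled blinded readings. Section 5.6 also lists Month 18, which is absent from the calendar and from 6.2; if it is kept, 8 × 45 = 360. The Month 18 entries need reconciling. Both counts assume that all 45 patients attend every visit, so they are upper limits for that number, and they measure workload rather than an effect on a result.

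**The case against.** The case against has several good parts.

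- **Late changes are already captured.** This stands for scarring, fibrosis and pigmentation change, which are recorded and graded as adverse events. It would be wrong to infer that late skin toxicity goes ungraded. It does not supply a blinded reading, and it does not name atrophy or telangiectasia.
- **Section 7 can be read more widely.** It opens with radiation-related toxicity in general, and each grade has a general severity definition that could be applied to a visible late change. Section 10.3 also counts pigmentation change among the signs of radiation dermatitis. This is fair, but neither the calendar nor section 7 tells the dermatologist to do so, and a single dermatitis grade would not show which change was present.
- **The scale is not described as acute only.** This stands. A reader might infer that the blinded grade cannot register any late damage, or that nearly all late readings would be grade 0. The documents support neither: necrosis and full-thickness ulceration carry no time limit, late erythema or edema could be graded, and no late-grade rates are given.
- **Little depends on it.** Section 2.1.1 reports the primary measure weekly during treatment, 8.1 evaluates endpoints at the last patient's Month 3 visit, 8.3 makes everything else exploratory, and the long-term objective (2.2.2.4) uses SkinDex16. All of this stands and limits the importance of the point.
- **The photographs could be re-read later.** They are de-identified and labelled by case number, so a blinded re-read is possible if they are retained. It would then use a scale chosen after the event; naming the items now avoids that.

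**Conclusion.** The point holds in a limited form. From Month 6 to Month 60 the plan specifies no blinded grading of any of the five late skin changes it names, and two of them, atrophy and telangiectasia, are named in no follow-up assessment. The other three reach the data as graded adverse events by a route not described as blinded. Up to 315 scheduled readings are affected (360 with Month 18).

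The primary endpoint and the Month 3 evaluation are untouched, and no one should conclude that the trial's main result is at risk. What is lost is a comparison of late skin toxicity, the stated purpose of the late visits, by an assessor who does not know the arm.

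This rests on two readings: that the calendar row, with section 7, defines what the dermatologist grades, and that an assessor not described as blinded may know the arm. It is a cheap improvement, not a flaw that must be corrected before the trial can be interpreted.

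**What to change.** 1. From Month 6, have the blinded dermatologist also grade, from the same photographs and under CTCAE version 5, atrophy, scarring, telangiectasia and pigmentation change. Keep the radiation dermatitis grade alongside.
2. Print the grade definitions for these items in section 7. The documents do not reproduce them, so the team should take them from the CTCAE manual. Where it has no specific term, state that the general severity definitions in section 7 apply.
3. Record a graded fibrosis item at the existing focused skin exam, and state that it is unblinded. Fibrosis therefore stays with an examiner who may know the arm; this change does not cure that.
4. Align 5.6, 6.1 and 7 so that all three name the same terms for the blinded reading.

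The photographs, visits and readers stay the same, and treatment and the primary endpoint are not touched. The cost is a revised grading form, one added exam item and a slightly longer reading of each late photograph.
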